3.2 Primary Study Endpoints

3.2.1 Phase I

Primary outcome screening measures in Phase I will be assessed at 10-treatment intervals which will equate to roughly every other week until the 30th treatment has been completed (see Table 4 for schedule of assessments). These outcome measures will provide an opportunity for mood ratings in the form of self-assessment (QIDS-A17-SR), a semi-structured clinical interview of the adolescent with input from parents (CDRS-R), and a clinical rating by the clinician of illness severity and improvement (CGI-S & I).

Furthermore, from a safety standpoint, suicidality will be carefully monitored on a weekly basis via the C-SSRS. Board certified/board eligible child and adolescent psychiatrists will administer all diagnostic assessments and clinical interviews determining study eligibility. Outcome measures assessing neurocognitive safety [the Children's Auditory Verbal Learning Test version 2 (CAVLT-2) and the Delis-Kaplan Executive Function Scale (D-KEFS)] will occur at baseline and at treatment completion and will be administered by trained psychometrists. These measures will be used in the assessment of any unanticipated change in cognitive function that may have occurred during the course of treatment. Inter-rater reliability exercises will be conducted for the CDRS-R to ensure intra-site and inter-site consistency of depression ratings.

3.2.2 Phase II, Arm 1

The schedule of primary outcome measures for Acute Treatment (Arm 1) of Phase II will be identical to that of Phase I with the exception that the End of Phase I assessments will be used for Phase II Baseline measures. See Table 5 for schedule of assessments.

3.2.3 Phase II, Arm 2

Primary outcome measures for Maintenance Treatment (Arm 2) in Phase II, including QIDS-A17-SR, CDRS-R, CGI-I, and CGI-S, will be assessed monthly. Suicidality will be carefully monitored on a monthly basis or more frequently as needed using the C-SSRS. Neurocognitive safety outcome measures (CAVLT-2 and D-KEFS) will be assessed at the completion of the maintenance treatments and at six-month follow-up. These will be

compared to Phase I Baseline and Phase I Completion assessments. See Table 6 for schedule of assessments.

3.3 Secondary Study Endpoints (MCR site only)

Secondary outcome measures will be collected for MCR subjects at baseline and at treatment completion (see Tables 4-6 for schedules of assessments). Imaging studies with ^1H -MRS at 3T will be utilized to study specific neurometabolic levels in the primary brain regions associated with major depressive disorder [AC (Brodmann's areas 24a/b and 32) and dorsolateral prefrontal cortex (Brodmann's 9/46)]. We also propose the investigation of the IC, an area of the brain thought to be related to integration of emotional and somatosensory inputs.[\[19\]](#)

3.4 Primary Safety Endpoints

The primary safety endpoint of this study is freedom from all treatment-related Unexpected Adverse Device Effects (UADEs) during the active treatment course and during the 6-month follow-up period. The definition of UADE is outlined in section 8.1 of the protocol.

3.5 Secondary Safety Endpoints

Secondary safety endpoints for this study include no statistically significant change (i.e. worsening) in cognitive performance as measured by the protocol-defined neurocognitive battery (D-KEFS and CAVLT-2). Neurocognitive assessments will occur at baseline, after the final treatment, and again six months following the final treatment. Measured outcomes at each time point will be compared with baseline scores to calculate change. (Wall, Baruth, Croarkin, et al. Submitted 2012). See Appendix C1 for copy.

4 Subject Selection, Enrollment and Withdrawal

Nearly 1,500 depressed adolescents (ages 13 to 18) are treated annually at Mayo Clinic in Rochester. Another 300-400 depressed adolescents are treated annually at MUSC in South Carolina. Approximately 40% of adolescents will not respond to currently available antidepressant or psychotherapeutic treatment approaches. Thus, annually, nearly 720-760 adolescents within the combined MCR and MUSC treatment areas would be potential rTMS treatment candidates. This protocol will plan to screen approximately 150 depressed adolescents (over three years) to enroll 75 subjects (50 at MCR and 25 at MUSC). Each site will plan to screen 5 adolescents per month for the study, with likely recruitment of 1-2 study subjects per month at each site. All adolescents meeting inclusion and exclusion criteria, as described in protocol Sections 4.1 and 4.2, will be offered participation in the study regardless of gender, race, or ethnicity. A strength of this multicenter collaboration is the ability to provide treatment to a more economically and ethnically diverse demographic population than would occur in the Rochester, MN, region alone.

Based on the most recent census data available (2010), Olmsted County, Minnesota, is primarily comprised of Caucasians (86%) of Non-Hispanic or Latino ethnicity (96%). African Americans and Asians each represent 5% of the total population. Females represent 51% of the population.

The Charleston County area in South Carolina population is primarily comprised of Caucasians (62%) of Non-Hispanic or Latino ethnicity (98%). The minority race population is represented by

African Americans (35%), Asians (1%), Other (1%), and Two or More Races (1%). Females represent 52% of the total population.

Therefore, we anticipate the distribution of gender (given the predominance of adolescent females with MDD), race, and ethnicity of enrolled subjects for the target 75 subjects, to be 25 males and 50 females; 3 Hispanic or Latino and 72 Non-Hispanic or Latino; 59 Caucasian, 11 African American, 3 Asian, 1 Other, and 1 Identified by two or more races. See Table 1.

All adolescents and their guardians will be provided a careful assent and consent discussion prior to enrollment. Since this is a sham-controlled trial, all subjects would need to understand that during Phase I of the trial, they will be randomized to either the active treatment condition or the sham treatment condition. They will also be informed about the opportunity to receive open, active rTMS treatment (during Phase II) if they did not have clinical response during Phase I.

Table 1 – Population Distribution and Estimated Enrollment Total and by Site

	Olmsted County, MN	MCR Site Enrollment	Charleston County, SC	MUSC Site Enrollment	Total Study Estimated Enrollment
Ethnicity					
Hispanic or Latino	4%	2	2%	1	3
Non-Hispanic or Latino	96 %	48	98%	24	72
	100%	50	100%	25	75
Race					
Caucasian	86%	43	62%	16	59
African American	5%	2	35%	9	11
Asian	5%	3	1%	0	3
American Indian / Alaska Native	0%	0	0%	0	0
Native Hawaiian / Pacific Islander	0%	0	0%	0	0
Other	2%	1	1%	0	1
Two or More Identified	2%	1	1%	0	1
	100%	50	100%	25	75

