Subject Participation Duration	Phase I (Randomized, Blinded): 6-8 weeks (Active rTMS vs. Sham) Phase II (Non-Randomized, Open-label): Acute Treatment (Arm 1) vs. Maintenance Treatment (Arm 2) Arm 1: 6-8 weeks of open-label acute treatment (for Phase I treatment nonresponders) Arm 2: 12 months of open-label, bi-weekly maintenance treatment (for Phase I treatment responders)
Objectives	1) To evaluate the antidepressant effects of daily, active rTMS (when compared with sham treatment) in adolescents meeting criteria for Major Depressive Disorder, single or recurrent episode (Phase I). 2a) To evaluate the benefit of daily, active, open-label rTMS in Phase I nonresponders (Phase II, Arm 1). 2b) To evaluate the benefits of bi-weekly, active, open-label maintenance rTMS treatment for Phase I responders over the course of 12 months post-acute treatment (Phase II, Arm 2). 3*) To evaluate, by proton magnetic resonance spectroscopy (¹ H-MRS) at 3 Tesla (3T), neurometabolic biomarkers at the beginning and end of each study phase. 3a. Define regional specificity [anterior cingulate (AC) and left dorsolateral prefrontal cortex (L-DLPFC)] of cerebral metabolites (i.e. glutamate and glutamine) in adolescent depression. 3b. Study whether specific neurochemical resonances are associated with response, remission, and/or maintenance of improvement of clinical depressive symptoms when rTMS is used to treat adolescent depression.
	*Assessed at MCR site only
Number of Subjects	Phase I: Total of 75 enrolled (38 Active/37 Sham) across both sites (50 at MCR; 25 at MUSC) Phase II: All treatment responders and nonresponders will be offered qualified follow-up treatments based on Phase I outcomes.
Diagnosis and Main Inclusion Criteria	Diagnosis of Major Depressive Disorder, single or recurrent, antidepressant treatment-resistant
Study Device	NeuroStar™ TMS System in XPLOR® research configuration

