4.4.2 Data Collection and Follow-up for Withdrawn Subjects

To enhance the validity of study data, as well as to provide subjects with ongoing monitoring and safety assessments by a qualified professional, subjects who choose to withdraw from the interventional portion of the study will be offered the opportunity to complete mood, cognitive, safety, and imaging assessments as per the study protocol.

5 Study Device

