6.2 Phase I – Randomized, Double-Blinded

Study Overview

Adolescents will be screened and enrolled in the study and randomized to either the active treatment or sham treatment group. Neither the subjects nor the investigators will know whether the treatments are active or sham in nature. All subjects will have baseline imaging for neurolocalization of L-DLPFC, mood, safety, and cognitive assessments. Subjects at the MCR site will have baseline magnetic resonance spectroscopy (MRS) at the time of the neurolocalization scan. All subjects will then undergo 30 rTMS treatments at their respective site within the 6- to 8-week timeframe. Mood, safety, and cognitive assessments will be performed at regular intervals throughout the study (Table 4). After the final treatment (i.e. treatment #30 or at early withdrawal), the mood and cognitive assessments will be performed for all subjects. MCR subjects will have MRS scans performed at these time points as well. These assessments may also occur monthly and at 6-month follow-up for those electing to not move on to Phase II treatment opportunities. The treatment and assessment schedules for Phase I are identical for both the active and the sham treatment cohorts. For participants at the MCR site, MRS scans will also occur after the final treatment and again at the 6-month follow-up visit.

Subjects may decline to complete any study assessment or measurement and still remain in the study so long as the assessment or measure in question does not directly impact the ability of study staff to conduct critical study procedures (ex. MRI for treatment localization, measures needed to determine eligibility, etc.) and does not impact the ability of study staff to assess the subject's continued safety (i.e., any of the Safety Assessments).

Table 4 – Phase I Schedule of Assessments (Active and Sham)

Day(s)	Pretreatment		6-Week Acute Treatment						Follow-Up	
	Screening	Baseline	Week 1 1-5	Week 2 6-10	Week 3 11-15	Week 4 16-20	Week 5 21-25	Week 6 26-30	Monthly 60, 90, 120, 150, 180	Final 210
Informed Consent	X									
KSADS	X									
Eligibility Checklist and Verification CRF	X									
Medical/Psychiatric History	X									
Urine Pregnancy Test	X									
Urine Drug Test	X									
Pre-TEEQ-P		X								
Pre-TEEQ-A		X								
Post-TEEQ-P								X ^g		
Post-TEEQ-A								X ^g		
Vital Signs ^{f,g,h,i}		X		X		X		X	X ⁱ	X
Mood Assessments										
CDRS-R ^{f,g,h}	X	X		X		X		X	X ⁱ	X
QIDS-A17-SR ^{f,g,h}	X	X		X		X		X	X ⁱ	X

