CGI-S ^{f,g,h}	X	X		X		X		X	X ⁱ	X
CGI-I ^{f,g,h}				X		X		X	X ⁱ	X
Y-MRS ^{f,g,h}	X	X	X	X	X	X	X	X	X ⁱ	X
C-VAS ^c			X	X	X	X	X	X		
Cognitive Assessments										
D-KEFS ^g			X					X		X
CAVLT-S ^g			X					X		X
Safety Assessments										
C-SSRS ^{d,f,g}	X	X	X	X	X	X	X	X	X	X
TASS	X									
Adverse Event Monitoring ^e			X	X	X	X	X	X	X	X
MRI Safety Screening Questionnaire			X					X ^g		X
Imaging Assessments										
MRI localization of L-DLPFC		X								
¹ H-MRS (MCR site only)		X						X ^g		X
TMS Procedures										
Motor Threshold Determination		X	X	X ^f	X	X ^f	X	X		
TMS Treatment ^a (5 days/week)										

Phase I Schedule of Assessments Footnotes

- a. Subjects are randomized to either the active or sham treatment arm prior to first TMS treatment in Phase I.
b. Motor threshold determination is conducted utilizing the unblinded, known-active treatment coil (Coil C).
c. C-VAS is performed daily pre- and post-treatment.
d. C-SSRS is performed weekly during treatment.

- e. Subjects are assessed daily for adverse events during treatment.
f. Assessed at the post-10 and post-20 treatment visit.
g. Assessed at the post-30 treatment visit OR at time of withdrawal for TMS treatment drop-outs.
h. Monthly follow-up assessments may be conducted via telephone
i. Optional monthly assessments

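### Section 3.5 counts a non-significant worsening on D-KEFS and CAVLT-2 as meeting the cognitive safety endpoint, with no margin, confidence-interval rule or stated sham contrast, so a real small-to-moderate decline can pass.

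*Combined protocol and SAP*

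**What the plan says.** Section 3.5 sets the endpoint: "Secondary safety endpoints for this study include no statistically significant change (i.e. worsening) in cognitive performance", measured by D-KEFS and CAVLT-2 at baseline, after the last treatment and six months later. Its only stated contrast is this: "Measured outcomes at each time point will be compared with baseline scores to calculate change". The test, its sidedness and whether it runs within or between arms are not given. The section ends by citing an unpublished manuscript (Appendix C1), which was not supplied.

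Section 3.2.1 says of the same tests: "These measures will be used in the assessment of any unanticipated change in cognitive function". It sets no threshold. Section 7.1 gives power for CDRS-R outcomes only. Section 7.2 has general treatment-group comparisons that name no endpoint, an exact test for adverse events, and secondary hypotheses about spectroscopy. Section 7.3 defines populations.

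Planned size in the Study Summary: "Total of 75 enrolled (38 Active/37 Sham) across both sites". On scheduling, Section 6.2 says: "The treatment and assessment schedules for Phase I are identical for both the active and the sham treatment cohorts". Footnote g to Table 4, attached to both tests, reads: "Assessed at the post-30 treatment visit OR at time of withdrawal for TMS treatment drop-outs".

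On completeness the text points both ways. Section 6.2 has the cognitive tests done for every subject at treatment end or early withdrawal. Section 4.4.2 says those who withdraw from treatment "will be offered the opportunity to complete mood, cognitive, safety, and imaging assessments as per the study protocol". Section 6.2 also says: "Subjects may decline to complete any study assessment or measurement and still remain in the study", with exceptions for critical procedures and Safety Assessments.

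**The concern.** A non-significant test does not show absence of harm. It may mean there is no decline, or that the decline was too small for the available precision. Section 3.5 gives both the same label. Where a true decline exists, fewer tested subjects or noisier scores raise the chance of meeting the endpoint.

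If change is tested only within the active arm, there is a second problem. Gains from retesting, or from improved mood, can offset a decline caused by treatment. The randomised sham arm, tested on the same schedule, would remove that bias, but Section 3.5 does not call on it.

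At stake is a report that cognition was safe in adolescents when the data could not exclude a small-to-moderate loss.

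**Working it through.** **The plan's own figures.** None is given for cognition. The Section 7.1 efficacy powers reproduce, so the sample sizes can be taken as stated.
- Continuous, 35 per arm: 8/(10·√(2/35)) = 3.35; Φ(3.35 − 1.96) = 91.7% (91.0% by noncentral t; stated 91%). At 25 per arm: 80.7% (79.1% by t; stated 80%).
- Binary, 65% v 25%, 35 per arm: (0.40 − 1.96·√(0.495/35))/√(0.415/35) = 1.53, giving 93.7% (stated 94%). At 25 per arm: 83.2% (stated 83%).

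**Inputs for cognition.** Alpha is 0.05 (Section 7.2). Sample sizes are 35 and 25 per arm (Section 7.1) and 38/37 (Study Summary). The documents give no effect size, so declines of d = 0.3, 0.5 and 0.8 SD of change are assumptions.

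**Chance of missing a true decline, one score.** This is 1 − P(t > t_crit) under noncentral t. The noncentrality is d·√n within arm (n − 1 df) and d/√(1/n1 + 1/n2) between arms (n1 + n2 − 2 df). Example: d = 0.3, n = 35 gives noncentrality 1.775, t_crit 2.032, miss rate 59.3%.

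| True decline | Within arm, n=38 / 35 / 25 | Versus sham, 38/37, 35/35, 25/25 |
|---|---|---|
| 0 | 97.5% at every n | 97.5% at every n |
| 0.3 SD | 56% / 59% / 70% | 75%, 77%, 82% |
| 0.5 SD | 15% / 18% / 33% | 43%, 46%, 59% |
| 0.8 SD | 0.2% / 0.4% / 3% | 7%, 9%, 21% |

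These are two-sided tests, counting significance in the worsening direction only. The zero row is the chance of passing when nothing has changed; one-sided it is 95%. One-sided, the 0.3 SD miss rates are 43-46% within arm and 64-66% against sham at 35 to 38 per arm.

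**More than one score.** Appendix E describes two D-KEFS tasks plus CAVLT-2, so assume three scores, with any significant worsening failing the endpoint and all three declining by 0.3 SD. Within arm at n = 35, uncorrected, the miss rate is 0.593³ = 21% if the scores are independent and about 40% at correlation 0.7. With Bonferroni it is about 43-59%. If only one score declines, it stays near 59%.

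**Retest gain.** Suppose harm relative to sham is 0.5 SD and retesting adds an assumed 0.2, 0.3 or 0.5 SD. The within-arm net decline is then 0.3, 0.2 or 0 SD, and the harm escapes at n = 35 with probability 59%, 79% or 97.5%.

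**Precision of active minus sham.** The 95% half-width is t(0.975)·√(1/n1 + 1/n2): 1.993 × 0.2310 = 0.46 SD at 38/37, 1.995 × 0.2390 = 0.48 SD at 35/35, and 0.57 SD at 25/25. Baseline adjustment multiplies this by √((1 + r)/2). With an assumed baseline correlation r of 0.5-0.8 and one fewer df, it is 0.40-0.44 SD at 38/37 and 0.41-0.45 SD at 35/35.

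**Margin excludable with 80% power** (no true difference, one-sided 0.025, unadjusted): 0.66 SD at 38/37 and 0.68 SD at 35/35.

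**The case against.** **No true change.** A reader might infer that poorer data always make the endpoint easier to meet. The documents do not support that. With no true change, one test passes 95-97.5% of the time whatever the sample size. Precision matters only if there is a real decline.

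**Missing assessments.** A reader might also infer that the plan lets cognitive data lapse. Section 6.2 says the tests will be done for all subjects at treatment end or early withdrawal. Whether they can be declined is unclear: Table 4 and Section 6.2.8 list them as Cognitive Assessments, but Section 3.2.1 calls them neurocognitive safety measures and Appendix E describes them under a joint cognitive and safety heading. What stands is that Section 4.4.2 only offers testing to those who withdraw, so numbers may fall. The 25-per-arm figures assume about 30% attrition with no withdrawn subject tested; they are an illustration, not a forecast or a floor.

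**One score.** The 59% figure is not the endpoint's overall miss rate. With several scores and no correction, a general decline is more likely to be caught.

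**Limited consequence.** The primary safety endpoint is unanticipated device effects (Section 3.4). Adverse events are asked about at every contact (Section 8.2), the DSMB includes a paediatric neuropsychologist (Section 8.6.1), and no stopping rule in the supplied text depends on Section 3.5. Group means and SDs are planned, so a reader could derive rough intervals. This limits the severity but leaves the endpoint's definition as it is.

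**Unseen material.** Appendix C1 might contain test and scoring detail. The absence of a rule can be asserted only for the text supplied.

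**Conclusion.** The point holds in a limited form. As written, Section 3.5 treats failure to detect worsening as the safety result, and nothing in the supplied text adds a margin, an interval rule or a sham contrast for cognition. Non-significance at the planned size would be informative about large losses: a 0.8 SD decline is missed under 1% of the time within arm and 7-9% against sham. It is weak evidence about 0.3 SD under either contrast, and about 0.5 SD against sham. These sizes assume one score, two-sided alpha 0.05 and effects in SDs of change; the three-score range shows how far the first assumption matters.

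A reader might go further and conclude that the trial will hide cognitive harm or that its overall safety assessment fails. The documents do not support that. This is a secondary endpoint in a pilot with separate safety monitoring, and the efficacy conclusion is unaffected. The change is still worth making, because the data for a better estimate are already scheduled.

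**What to change.** In Section 3.5, keep change from baseline by arm, including at six months, as descriptive results with 95% CIs. Then add wording such as:

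> The Phase I cognitive safety measure is the difference, active minus sham, in each named D-KEFS and CAVLT-2 score at the assessment after treatment 30 or at early withdrawal, adjusted for the baseline score and reported with its 95% CI and the number assessed in each arm. A non-significant difference will not be reported as showing no cognitive harm.

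These are estimates with no pass/fail rule, so no multiplicity correction is needed. If the sponsor wants to conclude absence of harm, it should name one deciding score and a margin before unblinding, knowing that before baseline adjustment a margin below about 0.66-0.68 SD could not be excluded with 80% power at 35 to 38 per arm.

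The cost is protocol wording only, with no new visits, tests or subjects. The downside is that the trial may have to report an inconclusive result where it could otherwise have reported no significant worsening.

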4.1 Inclusion Criteria

Table 2 – Inclusion Criteria

Inclusion Criteria	Determinant
Diagnosis of unipolar major depressive disorder, in a current major depressive episode, without psychotic features	K-SADS to confirm DSM-IV criteria
Pretreatment CDRS-R Raw score ≥ 40	CDRS-R
Age is at least 12 and less than 22 years	Self-report and review of medical record
Ongoing, stable dose antidepressant therapy for at least 6 weeks prior to active treatment to include the following antidepressants (with dosing range) Celexa (citalopram hydrobromide) – 10 to 60mg Cymbalta (duloxetine) – 40mg to 120mg Desyrel (trazodone HCl) – 12.5mg to 150mg Effexor (venlafaxine HCl) – 37.5mg to 300mg Luvox (fluvoxamine maleate) – 25mg to 200mg Lexapro (escitalopram oxalate) – 10mg to 40mg Paxil (paroxetine HCl) – 10mg to 50mg Pristiq (desvenlafaxine) – 50mg to 100mg Prozac (fluoxetine HCl) – 10mg to 80mg Remeron (mirtazapine) – 7.5mg to 45mg Zoloft (sertraline HCl) – 25mg to 200mg Savella (milnacipran HCl) – 25mg to 200mg	Physician evaluation and review of medical record
Subjects able to attend at least 31 study visits	Subject and family agreement
Willing to provide informed assent (adolescent) and informed consent (family)	Consent/assent discussion

4.2 Exclusion Criteria

Table 3 – Exclusion Criteria

Exclusion Criteria	Determinant
Subjects currently on a stimulant, antipsychotic, bupropion, or a tricyclic antidepressant medication.	Physician evaluation and review of medical record
Active substance use	Urine drug of abuse test (at screening)
Prior rTMS, vagus nerve stimulation (VNS), or ECT	Medical history
Contraindication to MRI	Physician evaluation; medical history; MRI Safety Screening Questionnaire
Contraindication to rTMS (history of neurological disorder such as seizures, increased intracranial pressure, brain surgery, or head trauma with loss of consciousness for >15 minutes, history of stroke, family history of epilepsy, intracardiac lines). Current anticoagulant, immune suppressive, and/or chemotherapy or those who have received any of these therapies within 3 months before enrollment in the study. Unstable medication conditions such as hematological or infectious (e.g., human immunodeficiency virus-HIV) disorders, implanted electronic device, metal in the head, or pregnancy.	Physician evaluation; medical history; MRI; urine pregnancy test (at screening)
History of schizophrenia, schizoaffective disorder, other (non mood disorder) psychosis, depression secondary to a medical condition, mental retardation, substance dependence or abuse within the past year (except nicotine), bipolar disorder, psychotic features in this or previous episodes, amnestic disorder, obsessive compulsive disorder, post-traumatic stress disorder, panic disorder	K-SADS to confirm DSM-IV criteria; Physician Examination and conference with family member/guardian to confirm findings; urine substance abuse survey (at screening)
History of autoimmune, endocrine, viral, or vascular disorder.	Physician evaluation; medical history
Unstable cardiac disease, uncontrolled hypertension, or sleep apnea	Physician evaluation; medical history
Active suicidal intent or plan, or history of attempt within the past 2 months	Physician evaluation
Any other relevant medical, personality, or psychosocial issues specific to the subject that the P.I. determines to be reason for exclusion from the study	Physician evaluation; medical history

